shock process. Administration of aldosterone in mice resulted in improved response to phenylephrine⁶. Based on the RCTs performed in human subjects, however, it is controversial whether addition of fludrocortisone provides any true benefit in refractory septic shock patients. Moreover, to date there has not been a trial, whether retrospective or prospective, that has directly compared the use of hydrocortisone alone versus the combination of hydrocortisone and fludrocortisone. Because of this lack of data, we will be investigating the use of hydrocortisone alone versus the combination in critically ill septic shock patients admitted to the medical intensive care unit. Currently, both are considered standard of care both within and outside of the University of Tennessee Medical Center Knoxville.

Objective: To determine if the use of hydrocortisone plus fludrocortisone is associated with a faster resolution of shock (defined as 24 hours vasopressor free) when compared to the use of hydrocortisone alone in medical, critically ill septic shock patients

Study Design and Methods:

This study is a single-center, prospective, open-label, randomized trial which will evaluate adult patients admitted with septic shock to the medical critical care unit (MCC).

Inclusion Criteria:

- Age \geq 18
- Critically ill medicine patients requiring addition of stress dose steroid therapy (hydrocortisone) in addition to pressors for septic shock management during their ICU stay
- Fludrocortisone administered within 24 hours after initiation of hydrocortisone if in combination therapy group

Exclusion Criteria:

- Use of fludrocortisone and/or hydrocortisone for any reason other than septic shock management during ICU stay
- Fludrocortisone/hydrocortisone initiated by any service other than critical care medicine
- Prior use of fludrocortisone/hydrocortisone at time of admission (home or outside facility)
- Patients not appropriate for study inclusion as determined by provider discretion
- Patients receiving steroid therapy not in accordance with assigned group per location (MCC1 or MCC2)
- Patients re-admitted to the MCC during the same admission and restarted on vasopressor therapy will be noted during data collection and only the initial admission will be included for analysis
- Any patient receiving greater than one dose of hydrocortisone 100 mg
- Physical or medical contraindication to receiving PO or PER FT (per feeding tube) fludrocortisone.

Protocol:

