All patients admitted to the medical critical care unit side 1 (MCC1) or side 2 (MCC2) will be provided a “Notice of Research.” At any time, refusal or withdrawal from the study can be requested by the patient, patient advocate, or provider.

Patients that meet inclusion criteria for the study will receive either hydrocortisone 50 mg IV Q6h alone or a combination of hydrocortisone 50 mg IV Q6h plus fludrocortisone 50 mcg PO/PER FT daily. Fludrocortisone must be initiated and administered within 24 hours after the first administered dose of hydrocortisone. Because fludrocortisone is only available as a 100 mcg tablet, the nurse at the bedside will split the tablet into two as to provide a 50 mcg dose. This is standard of practice currently when fludrocortisone is utilized in our institution.

Steroid therapy assignments will be randomized based on patient location. For three consecutive months starting in October 2018, all patients in MCC1 will receive hydrocortisone alone and all patients admitted to MCC2 will receive hydrocortisone plus fludrocortisone. Then, in the following three consecutive months, this will be flipped and MCC1 will receive hydrocortisone plus fludrocortisone while MCC2 will receive hydrocortisone alone. This change in group assignments will occur to account for the difference in number of beds between MCC1 and MCC2, and to minimize the potential differences in patient acuity by location.

Initiation of hydrocortisone for inclusion in the study will be determined solely by provider discretion as the standard of care for septic shock patients. Once hydrocortisone is initiated, fludrocortisone will be initiated within 24 hours for patients on the qualifying side of the unit, unless any of the previously stated exclusion criteria are present. Because these interventions are currently utilized and considered standard of care in the MCC, data collection will be performed retrospectively by generating a list of patients in the MCC receiving hydrocortisone therapy.

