 - Reinitiation of vasopressor therapy (after vasopressor free for 24 hours)
 - Reinitiation of hydrocortisone and/or fludrocortisone
 - Mechanical ventilator free days during ICU admission
 - Duration of steroid therapy
- Safety Endpoints
 - Documentation of two consecutive point of care blood glucose checks >180 mg/dl after initiation of hydrocortisone and/or hydrocortisone/fludrocortisone
 - Gastrointestinal bleed during study period (as documented by provider)
 - Severity of bleed as determined by GUSTO criteria
 - Severe: deadly bleeding; intracerebral bleeding or substantial hemodynamic compromise
 - Moderate: bleeding requiring transfusion
 - Mild: other bleeding not requiring transfusion or causing hemodynamic compromise
 - New initiation of renal replacement therapy during study period
 - Electrolyte abnormalities
 - Sodium level greater than 150 mEq/L during study period
 - Potassium level greater than 5.5 mEq/L during study period

Other Data Collected:

- Demographics: Age, sex, weight, height, BMI, ethnicity (race)
- Septic Shock Bundle initiated
- WBC at time of steroid initiation and at discontinuation

- Initial lactic acid level on admission
- Lactic acid level at initiation of vasopressors
- Vasopressor initiated (norepinephrine, epinephrine, phenylephrine, vasopressin, dopamine, dobutamine)
- Vasopressor dose when steroid therapy was initiated (mcg/min and mcg/kg/min)
- Max vasopressor dose during study period
- SOFA Score
- APACHE Score
- Charlson Comorbidity Index
- Site of infection (lung, intraabdominal, urogenital, skin, CNS, endocarditis, bacteremia, unknown, etc.)
- Non-contaminant, positive culture during study period with clinical correlation to septic shock event
 - Site of culture
 - Gram Positive
 - Gram Negative
 - Viral
 - Fungal
 - Organism
- Comorbidities:
 - Documented heart failure
 - Documented chronic kidney disease stage III-IV not requiring renal replacement therapy at baseline
- Documentation of concurrent cardiogenic shock during study period
- Serum creatinine at initiation of steroid therapy
- Serum creatinine at discontinuation of steroid therapy
- Renal replacement therapy at the initiation of steroid therapy
- Mechanical ventilation at initiation of steroid therapy
- Other systemic steroid use (methylprednisolone, dexamethasone, prednisone) prior to pressor initiation
- Systemic steroid use prior to admission (home medication)

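### Entry rests on a discretionary hydrocortisone start made with the arm already known; no adjustment for severity is prespecified as primary, and starts and exclusions by arm are not counted

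*Combined protocol and SAP*

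**What the plan says.** - **Entry.** The Inclusion Criteria admit "Critically ill medicine patients requiring addition of stress dose steroid therapy (hydrocortisone) in addition to pressors for septic shock management during their ICU stay". No vasopressor dose, duration or blood pressure threshold is given. Under Protocol, "Initiation of hydrocortisone for inclusion in the study will be determined solely by provider discretion".
- **Arm known beforehand.** The study is a "single-center, prospective, open-label, randomized trial". In the first three months "all patients in MCC1 will receive hydrocortisone alone and all patients admitted to MCC2 will receive hydrocortisone plus fludrocortisone"; the sides then swap for three months. The stated reasons for the swap are bed numbers and patient acuity by location.
- **Second discretionary filter.** The Exclusion Criteria list "Patients not appropriate for study inclusion as determined by provider discretion", without saying when the judgement may be made or that reasons are logged. Separately, the Protocol section lets the patient, an advocate or the provider request refusal or withdrawal at any time.
- **Case finding.** Data come from "generating a list of patients in the MCC receiving hydrocortisone therapy". No list of vasopressor-treated patients who were not started is described.
- **Severity data.** Other Data Collected includes vasopressor dose at steroid start, SOFA, APACHE, and lactate on admission and at vasopressor start.
- **Analysis.** Statistical methods compares continuous outcomes by t-test or Mann-Whitney test. It also plans a multiple regression with time to resolution of shock as outcome, without naming covariates or calling it primary.
- **Limitations.** Open label, no placebo and documentation bias are acknowledged. Selection at entry is not.

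**The concern.** Whoever decides that a patient enters already knows which regimen entry brings. If the threshold for starting hydrocortisone, or for judging a patient unsuitable, differs with the regimen in force, the arms differ in severity before treatment begins. Time to resolution of shock can then differ with no effect of fludrocortisone, or a real effect can be masked. Background and Rationale calls the added benefit of fludrocortisone controversial, and treats severity at enrolment as one of the two main differences between trials with and without a mortality benefit. So providers may hold views on the combination, and severity at entry plausibly matters to outcome. The group comparison as written would carry any such imbalance straight into the result.

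**Working it through.** **The plan's own figure.** Statistical Power gives means of 96 and 72 h, SD 36, two-sided alpha 0.05, and 39 per group. Power is not stated; 80% is assumed here.

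- Normal formula: n = 2 × (1.96 + 0.84)² × (36/24)² = 35.3, so 36 per group.
- Exact t-test: 37 per group. Dividing by the Mann-Whitney efficiency of 0.955 gives 37/0.955 = 38.7, so 39, which matches.
- t-test power at 39 per group is 82.8%.

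The sample size is not at issue; n = 39 and SD = 36 are carried forward.

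**Does the switch cancel the problem?** Let δ be the drug effect, s1 and s2 the stable effects of the two sides, and b a shift caused by an arm-dependent starting threshold. The combination-minus-alone difference is:

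- first block: δ + b + (s2 − s1)
- second block: δ + b + (s1 − s2)
- average of the two: δ + b

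The side difference cancels when the blocks are weighted equally. The selection shift b does not, because it moves with the regimen.

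**How large could it be?** The documents give no figure, so the inputs are assumed. A fraction f of one arm are extra, milder patients whose shock is m hours shorter, and there is no drug effect. For scale, 36 h is one planned SD and 48 h is half the larger planned mean.

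Shift in arm mean = f × m. Mixing also widens that arm's SD to √(36² + f(1 − f)m²); for f = 0.3 and m = 48 this is √(1296 + 483.84) = 42.2 h. Rejection rates of the two-sided t-test at 39 per arm, from 20,000 simulated trials per cell:

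| f | m = 24 h | m = 36 h | m = 48 h |
|---|---|---|---|
| 10% | 2.4 h: 5.9% | 3.6 h: 7.1% | 4.8 h: 8.5% |
| 20% | 4.8 h: 8.7% | 7.2 h: 13.2% | 9.6 h: 19.0% |
| 30% | 7.2 h: 13.6% | 10.8 h: 23.5% | 14.4 h: 35.8% |

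Over m = 36 to 48 h, the shift is 3.6 to 14.4 h, or 15% to 60% of the planned 24 h difference. Holding the SD at 36 would overstate the rates: 14.1%, 21.4% and 41.5% where the table has 13.2%, 19.0% and 35.8%.

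**Opposite direction.** With a true 24 h effect and SD 36, an adverse shift of 6 h leaves a difference of 18 h and cuts power from 82.8% to 58.7%.

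**What the planned data can and cannot show**

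| Question | Answerable as planned? |
|---|---|
| Are included patients milder in one arm on measured severity? | Yes, though no baseline comparison by arm is explicitly specified |
| What share of vasopressor-treated septic shock patients was started, by arm? | No; those not started are not listed |
| How many were excluded by discretion in each arm, and why? | No log is described |
| Do the arms differ in unmeasured severity? | No |

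**The case against.** Four points can be made for the plan.

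1. **Nothing shows that starts depend on the arm.** Both arms receive hydrocortisone, and the protocol calls both regimens standard of care. The decision in question is whether to start the drug common to both. This stands: a reader might infer that the comparison is biased, but the documents support only a risk.
2. **Severity is recorded.** A reader might infer that nothing planned would reveal selection. That is too strong: SOFA, APACHE, lactate and vasopressor dose at steroid start would show milder included patients in one arm. What stays hidden is start rates, discretionary exclusions and unmeasured severity.
3. **An adjusted analysis is planned.** A reader might infer that there is none, but Statistical methods includes a multiple regression on the primary outcome. The remaining criticism is that its covariates and its status are left open, so they could be chosen after the data are seen.
4. **The direction is uncertain.** The Outcomes section gives no time origin for the primary endpoint. If time ran from steroid start, an earlier start could lengthen the measured time rather than shorten it. This also stands, and is why both directions are shown above.

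Concealment is not feasible with allocation by location, and the point does not ask for it.

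**Conclusion.** The concern holds as a risk that the plan neither measures in full nor commits to adjust for. Entry is discretionary with the arm known, a second discretionary exclusion has no time limit, and the switch of sides does not cancel a starting threshold that follows the regimen. The false-positive rate of about 7% to 36% rests entirely on assumed fractions (10% to 30%) and differences (36 to 48 h), together with the plan's SD of 36 and 39 per arm. At the mild end the effect is small, and with no arm-dependent selection it is nil. The documents do not support saying that bias has occurred, which way it would run, or that it would be wholly invisible. Because the main adjusters are already collected, a prespecified adjusted comparison improves on the unadjusted test at little cost.

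**What to change.** 1. **Primary analysis.** Make the primary comparison a prespecified regression of time to resolution of shock on arm, adjusted for vasopressor dose at steroid start, SOFA, lactate at vasopressor start, unit side and period. Report the severity values by arm. SOFA is listed without a time point, so fix it at or before steroid start. Arm remains estimable alongside side and period because the sides switch.
2. **Starts.** From the MCC records, report by side and period the number of septic shock patients on vasopressors, the proportion started on hydrocortisone, and the time to start.
3. **Exclusions.** Count discretionary exclusions by arm with reasons. Do not let a discretionary judgement made after the first hydrocortisone dose remove a patient from the analysis. The right to withdraw from the study, and provider judgement over treatment, stay as they are.

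An outcome analysis of all vasopressor-treated patients is not needed: it would include patients given neither regimen, which dilutes the contrast, and would require more chart review.

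**Cost.** Some chart abstraction is needed to confirm septic shock in patients not started on hydrocortisone. The five covariates, at one term each, reduce residual degrees of freedom from 78 − 2 = 76 to 78 − 7 = 71. Treatment and allocation are unchanged.

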While each included patient’s data will be recorded retrospectively after randomization, we do believe that it is necessary to perform this study in a prospective manner rather than fully retrospective. It is not feasible to perform this study retrospectively as we would not be able to ensure adequate and equal numbers in each group within the medical critical care unit, especially considering how medical critical care patients are placed in other intensive care units within our institution based on bed availability. Unequal groups would unduly bias the results and make the analysis less meaningful in terms of contributing to the current body of evidence.

Any medication events, including adverse drug reactions or medication errors, will be routinely reported throughout the study to the UTMC Safety Intelligence system. Routine reports of events related to the study will be reviewed weekly by our medication safety office if necessary. Data will be collected continuously throughout the study duration and investigators will review the data for any concerning safety or efficacy differences between the treatment groups. Upon regular screening for adverse drug events, if any are detected, they will be not only be reported to the Safety Intelligence system but will also be reported for review by the IRB.

Per the FDA guidance for clinical investigators regarding the need for an investigational new drug (IND) application in human research studies, investigations are exempt if the drug is lawfully marketed in the U.S., the investigation is not intended to support a new indication or change the labeling of the drug, the investigation will not support a change in advertising for the drug, and the route of administration, dose, or any other factor of the investigation will not increase the risk associated with the drug⁷. Our study, since we are not changing standard of care and are using accepted, studied doses of hydrocortisone and fludrocortisone, meet these criteria for exemption from IND application.

Outcomes:

- Primary Endpoint:
 - Time to resolution of shock (defined as 24 hours vasopressor free)
- Secondary Endpoints:
 - ICU Length of Stay (LOS)
 - Hospital LOS
 - All-cause mortality at ICU discharge
 - All-cause mortality at hospital discharge
 - All-cause mortality at 28 days of admission
 - All-cause mortality at 90 days of admission
 - Withdrawal of treatment therapy during ICU stay

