- Continuation of baseline/prior steroid in combination with hydrocortisone/fludrocortisone
- Inhaled corticosteroid use
- Intubation with etomidate
- Amount of diuretics received during study period
- Acute respiratory distress syndrome documented during study period
- Administration of neuromuscular blocker during study period

Statistical Analysis:

Statistical Power

In order to achieve adequate statistical power for the proposed prospective trial, an a priori sample size calculation was completed based on an evidence-based measure of effect size from the APROCCHSS and CORTICUS trials^{3,4}. The evidence-based difference between the treatment groups was 24 hours (Group 1 $M = 96$, $SD = 36$; Group 2 $M = 72$, $SD = 36$), leading to a Cohen's d effect size of 0.67. With a two-tailed hypothesis, an effect size of $d = 0.67$, an alpha value of 0.05, and equal allocation to treatment groups (1:1), 39 participants would be needed for each treatment group. This means the total sample size will be $n = 78$ in order to achieve adequate statistical power for the trial.

Statistical methods

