Frequency and percentage statistics will be used to analyze categorical demographic, predictor, confounding, and outcome variables of interest for the sample. Descriptive statistics will be used to describe the sample characteristics associated with continuous variables. The assumption of normality of continuous distributions will be assessed using skewness and kurtosis statistics. If either statistic is above an absolute value of 2.0, then the distribution will be assumed to be non-normal. Homogeneity of variance between independent groups will be tested using Levene's Test for Equality of Variances. When both statistical assumptions are met, independent samples t-tests will be used to compare the treatment groups on continuous outcomes. Means and standard deviations will be reported and interpreted for these analyses. Mann-Whitney U tests will be used for comparisons when statistical assumptions are violated. Medians and interquartile ranges will be presented and analyzed for non-parametric comparisons. Chi-square tests will be used to test for significant associations between the treatment groups and categorical outcomes. Relative risk with 95% confidence intervals will be reported for significant categorical associations. Multiple regression analysis will be performed with time to resolution of shock as the outcome. Linearity, normality, homoscedasticity, multicollinearity, and autocorrelation assumptions for the regression analysis will be performed. Unstandardized beta coefficients, standard errors of the coefficients, and standardized beta coefficients will be reported and interpreted, along with the change in shared variance (R^2) and respective F-tests. All analyses will be conducted using SPSS Version 22 (Armonk, NY: IBM Corporation) and statistical significance will be assumed at an alpha value of 0.05.

A priori subanalysis will be performed on the following subset of patients: documented history of heart failure and documented chronic kidney disease stage III and IV requiring renal replacement therapy at baseline.

Critical Analysis/Limitations:

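### ICU and hospital length of stay are tested with no rule for patients who die, so an early death counts as a short stay and can favour the arm with more deaths

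*Combined protocol and SAP*

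**What the plan says.** Under Outcomes, the secondary endpoints include "ICU Length of Stay (LOS", hospital stay and "Duration of steroid therapy". None has a definition or a rule for death. Death is counted separately, for example as "All-cause mortality at ICU discharge" and "All-cause mortality at hospital discharge", with further counts at 28 and 90 days of admission.

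Under Statistical methods, when normality and equal variance hold, "independent samples t-tests will be used to compare the treatment groups on continuous outcomes". Otherwise, "Mann-Whitney U tests will be used for comparisons when statistical assumptions are violated". That is the only between-arm method given for continuous secondary endpoints.

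There is no survivors-only analysis, no worst-rank or free-days score for death in these endpoints, and no censoring or competing-event method. The one free-days outcome, for mechanical ventilation, also has no stated score for death. The limitations section does not raise the matter.

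**The concern.** Death ends an ICU stay just as discharge does. A patient who dies on day 2 has a recorded stay of 2 days, and a t-test or rank test treats that value like a discharge in good health on day 2. Two conditions turn this into bias: mortality must differ between the arms, and deaths must come earlier than survivors' discharges.

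The plan treats the first condition as open. The background asks whether the regimens differ in mortality, and four mortality endpoints are listed. Allocation is by side of the unit, and the Protocol section acknowledges possible differences in acuity by location. If both conditions hold, a shorter stay may reflect excess deaths rather than faster recovery.

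**Working it through.** **Inputs from the plan.** 39 per arm, 1:1, alpha 0.05 ("an alpha value of 0.05, and equal allocation to treatment groups (1:1), 39 participants would be needed for each treatment group"), two-sided ("With a two-tailed hypothesis").

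**The plan's own figure.** The sample size concerns only the primary endpoint. The power is not given as a number, so 80% is assumed here. With d = 24/36 = 0.667, a t-test needs 36.3, so 37 per arm. Dividing by the Mann-Whitney efficiency 3/π = 0.955 gives 36.3/0.955 = 38.02, so 39 per arm and 78 in total, as stated. This fixes the 39 used below and has no other bearing on the point. No figure is stated for length of stay.

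**Assumed inputs (not in the documents).** Stays are lognormal with CV 0.7. Survivors' mean is 12 d in both arms, so there is no true effect on survivors' stay. Decedents' mean is 4 d.

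**Mean stay.** With mortality p, mean stay = (1 − p) × 12 + p × 4. The difference between arms is therefore (difference in p) × (12 − 4).
- 35%: 0.65 × 12 + 0.35 × 4 = 7.8 + 1.4 = 9.2 d
- 40%: 0.60 × 12 + 0.40 × 4 = 7.2 + 1.6 = 8.8 d
- 45%: 0.55 × 12 + 0.45 × 4 = 6.6 + 1.8 = 8.4 d
- 55%: 0.45 × 12 + 0.55 × 4 = 5.4 + 2.2 = 7.6 d

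**Wrong-direction significance.** This is the simulated share of trials in which a two-sided Mann-Whitney test at 0.05 finds a significantly shorter stay in the higher-mortality arm. With no bias it would be 2.5%.

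| Mortality | Mean stay | Apparent gain for higher-mortality arm | Wrong-direction significance |
|---|---|---|---|
| equal | equal | 0 d | about 2.5% |
| 40% v 45% | 8.8 v 8.4 d | 0.4 d | about 5% |
| 35% v 45% | 9.2 v 8.4 d | 0.8 d | about 8% (7% to 9% in repeat runs) |
| 35% v 55% | 9.2 v 7.6 d | 1.6 d | about 22% |

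**Timing of death.** At 35% v 55%, the rate is about 26% if decedents' mean stay is 3 d, 13% at 6 d, 7% at 8 d, and back to the nominal 2.5% at 12 d, where deaths come as late as discharges.

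**A second set of assumptions.** Survivors' median 10 d, decedents' median 3 d, log-SD 0.7. The rate is about 9% at 35% v 45%, 22% at 30% v 50% and 43% at 25% v 55%. With decedents' median at 5 d it is about 6%, 11% and 22%. At 10 d there is no bias.

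**Scoring death as unfavourable.** In the first set, at 35% v 55%, mean ICU-free days to day 28 (death = 0) are 10.7 v 7.4, in favour of the lower-mortality arm. Significant results for the higher-mortality arm fall to under 0.1%. In the second set (decedents' median 3 d, death ranked worst) they fall from 8.5% to 0.4% at 35% v 45%, and with equal mortality the two-sided error stays near 5%.

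**The case against.** **The large figure needs a large mortality gap.** This stands. The 22% rests on an assumed 20-point difference. At 5 to 10 points the rate is about 5% to 8%, and with equal mortality or late deaths there is no bias. Chance imbalance still occurs: with 40% true mortality in both arms, two groups of 39 differ by 4 or more deaths in about 42% of trials. Averaged over trials that does not raise the error rate, but it can colour the result of a single trial.

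**Mortality is reported alongside.** A reader might infer that a difference in stay could never be interpreted. The documents do not support that. Four mortality endpoints are reported, and at 35% v 55% a chi-square test on mortality would itself be significant in about 44% of trials, so the conflict would often be visible. Seeing it does not correct the test on stay.

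**Much is inferred from silence.** The plan does not say that all patients enter the comparison. That follows from the general rule for continuous outcomes and the absence of any restriction. Nor does it say that a shorter stay is better; raw stay in all patients is a legitimate measure of resource use. The error arises when it is read as patient benefit.

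**Two further readings go too far.** Listing four mortality endpoints does not show that many deaths are expected, since it says nothing about the death rate. And although death also truncates steroid duration, the plan gives that endpoint no favourable direction. It can be read as treatment exposure.

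**Conclusion.** The concern holds for ICU and hospital stay. Followed as written, the plan counts an early death as a short stay, and its test can point the wrong way. This is a conditional bias, not a demonstrated reversal: it needs unequal mortality and deaths earlier than discharges. Under the first set of assumptions, wrong-direction significance runs from the nominal 2.5% to about 22%, and the spurious difference in mean stay from 0 to 1.6 d. All mortality and length-of-stay inputs are assumed.

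These are secondary endpoints for which the trial was not sized, and the primary conclusion does not depend on them. The change is worth making because it is cheap. For steroid duration, only the reporting needs attention.

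**What to change.** 1. Make the between-arm comparison of ICU and hospital stay one in which death is not a favourable value: ICU-free and hospital-free days to day 28, with death by day 28 scored 0, compared by a rank test. Time to discharge alive, with death as a competing event, is an acceptable alternative. Choose one in advance.
2. State one day-28 clock and align it with the 28-day mortality endpoint, which is counted from admission. Say whether hospital or unit admission is meant.
3. State how ICU readmissions within 28 days count. The exclusion criteria keep only the initial admission for patients readmitted to the unit and restarted on vasopressors, so later ICU days might otherwise be lost.
4. Report raw ICU and hospital stay descriptively, split by survivors and decedents.
5. Report steroid duration also by survival status, as treatment exposure, without reading shorter as better.

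The cost is a short addition to the Outcomes and Statistical methods sections, with no change to treatment or sample size. There are small downsides. Raw stay is no longer the tested outcome. Free days partly reflect mortality, which is already tested, and also give 0 to survivors still in hospital at day 28. Date of death is not a listed data item, so it, or 28-day status, must be recorded on the same clock.

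### On the natural reading, vasopressor restarts that bring a patient back to the MCC are noted but not counted in the secondary relapse endpoint

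*Combined protocol and SAP*

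**What the plan says.** Under Outcomes, Secondary Endpoints, the plan lists "Reinitiation of vasopressor therapy (after vasopressor free for 24 hours") and, on the next line, "Reinitiation of hydrocortisone and/or fludrocortisone". Neither has a time window or a location. A nearby item does have one: "Mechanical ventilator free days during ICU admission".

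Under Study Design and Methods, Exclusion Criteria, the plan says: "Patients re-admitted to the MCC during the same admission and restarted on vasopressor therapy will be noted during data collection". The same sentence goes on to say that "only the initial admission will be included for analysis".

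The primary endpoint, under Outcomes, is "Time to resolution of shock (defined as 24 hours vasopressor free"), so it uses the same 24-hour threshold as the relapse endpoint. For outcomes of the yes/no kind, Statistical methods says: "Chi-square tests will be used to test for significant associations between the treatment groups and categorical outcomes".

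**The concern.** Relapse is the natural check on the primary endpoint, because faster resolution means less if shock then returns. The readmission rule sets aside patients who, in large part, are having the relapse event. Suppose two patients each come off vasopressors for 24 hours and each later restart. The one still in the unit is an event. The one who had left the unit and came back is, on the natural reading, not an event.

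Time under observation for relapse would then depend on unit discharge. Discharge happens after assignment, the trial is open-label, and ICU length of stay is itself a secondary endpoint. An arm whose patients leave the unit sooner after resolution would have less time in which a restart could count, and a chi-square test makes no allowance for that.

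**Working it through.** There is no relapse rate, readmission rate or power statement for this endpoint, so there is no figure of the plan's to reproduce. The check is a comparison of texts, followed by an illustration on assumed rates.

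**Texts side by side**

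| Situation after 24 h off vasopressors | Recorded? | Counted as reinitiation? |
|---|---|---|
| Restart during the first MCC stay | Yes | Yes |
| Restart with return to the MCC, same hospital stay | Yes, the rule says it is noted | No, on the natural reading |
| Restart in another ICU of the hospital | Not addressed | Not addressed |
| Steroid restart together with a vasopressor restart on MCC return | Falls under the same rule | No, on the natural reading |
| Steroid restart without a vasopressor restart | Not addressed by the rule | Not addressed by the rule |

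The third row is a real possibility, because the Protocol section says that medical critical care patients are also placed in other ICUs according to bed availability. Nothing in Outcomes or Statistical methods exempts the relapse endpoint from the readmission rule or limits it to the first unit stay.

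**Illustration (all rates assumed; none is in the documents)**

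Let p be the true relapse proportion in an arm and f the share of relapses that occur after unit discharge and are dropped. The counted proportion is p × (1 − f).

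1. Equal loss. Take p = 30% versus 15%, and 39 per arm (the planned group size; the number who reach resolution would be smaller).
   - Expected events with nothing dropped: 39 × (0.30 + 0.15) ≈ 17.5.
   - With f = 25% in both arms: counted 22.5% versus 11.25%, and 39 × (0.225 + 0.1125) ≈ 13.2 events. The difference shrinks from 15 to about 11.3 points.
   - With f = 10% or 50%: 15.8 or 8.8 events, and a difference of 13.5 or 7.5 points.
   - The ratio of the two arms stays at 2.0; events and precision are lost.

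2. Unequal loss, no true difference. Take p = 25% in both arms, f = 10% in one and 40% in the other.
   - Counted: 0.25 × 0.90 = 22.5% and 0.25 × 0.60 = 15.0%.
   - Apparent relative risk: 15.0 / 22.5 = 0.67, or 22.5 / 15.0 = 1.5 if the arms are swapped.

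3. Unequal time in the unit, no true difference. Take a constant 2% daily restart risk in both arms, ignoring death, with 1 versus 3 unit days after resolution.
   - Counted: 1 − 0.98 = 2.0% and 1 − 0.98³ = 5.9%.
   - Apparent relative risk: 2.0 / 5.9 = 0.34.

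Cases 2 and 3 show that unequal loss alone can create a difference. They do not show that the loss will be unequal in this trial.

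**The case against.** The strongest defence is that the rule sits under Exclusion Criteria and is there to stop one patient entering twice. That purpose is sound. The plan never says in terms that a returning patient is scored as having no reinitiation. The word *admission* is also used loosely: earlier in the same sentence it means the hospital stay. And since these readmissions are noted, the investigators may intend to use them for this endpoint.

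Much of this stands. The wording is slightly ambiguous, and the gap is in the analysis rule, not in data capture. But the stays being set aside are MCC readmissions, so the first MCC admission is the natural reading of what is kept. One record per patient does not require discarding that patient's later events.

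Three stronger readings are tempting and are not supported:

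- A reader might infer that every steroid restart after unit discharge is lost. The rule covers only patients who return and restart vasopressors; a steroid restart without that is not mentioned.
- A reader might infer that the rule favours the combination arm, or any particular arm. The documents contain nothing on time to unit discharge or readmission by arm.
- A reader might take an illustrative figure as an estimate of the share of relapses missed. Any such share follows from assumed unit days, ward days and daily risks, and the documents supply none of them.

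It is also fair to say that an outcome confined to the index stay is legitimate if it is labelled that way, and that this is one of many secondary endpoints in a trial sized for the primary.

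**Conclusion.** The point holds for a secondary endpoint. A stated analysis rule, read naturally, removes true relapse events from an endpoint that is meant to count them, and it ties the length of observation to unit discharge. Steroid reinitiation shares the problem only where it accompanies a vasopressor restart on return to the MCC. Restarts during the first MCC stay still count.

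The size of the effect is unknown. If the loss is equal in the two arms, the cost is fewer events and a smaller absolute difference; if it is unequal, the comparison is distorted in a direction that cannot be foretold. A reader might infer that the main result is at risk. It is not: one record per patient is right for time to resolution, and neither the primary endpoint nor the sample size of 78 changes.

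The conclusion rests on one assumption: that the admission kept for analysis is the first MCC stay. If the investigators meant the whole hospital stay, a sentence saying so would remove the conflict, though the window would still need stating.

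**What to change.** 1. In Exclusion Criteria, state that the first MCC admission is the single record per patient for the primary endpoint, and that a vasopressor restart on return to the MCC in the same hospital stay, with any accompanying steroid restart, counts as a reinitiation event in the originally assigned arm.
2. In Outcomes, give the endpoint a window of the same number of days from each patient's own resolution of shock, for example 14. Counting from resolution gives patients the same nominal time at risk. A limit set from the first steroid dose would give more time to those who resolve sooner, and a limit at hospital discharge would again depend on a decision made after assignment.
3. Count restarts recorded in any ICU of the hospital during the same stay.
4. Report, by arm, deaths and hospital discharges before the window closes. The endpoint can occur only in patients who reached resolution, so give that number by arm as well.
5. Also report the count restricted to the initial MCC stay, labelled as such.

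The cost is small: a sentence or two in each of the two sections, and use of readmissions that are already to be noted. Restarts in other ICUs need an extra look in the record, since the current note covers only returns to the MCC. There are two modest downsides. Some late restarts will be new shock episodes. And because the regimen follows the side of the unit and switches after three months, some patients will return to a side, or in a period, assigned the other regimen. Both groups should be listed separately.
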